7.4 Diet, Fluid, and Activity Control

The investigator or study collaborator should instruct subjects on the following items:

1. The subject must be punctual for visit, undergo physical examination and predefined examinations. If the subject cannot visit, he/she should inform the investigator or study collaborator as soon as possible.
2. If the subject experiences a worsening of conditions on any day the site visit is not scheduled, he/she should inform the investigator or study collaborator of the worsening by telephone or other manners as soon as possible and seek instructions.
3. The subject must take the study medication as instructed by the investigator. If the subject is noncompliant with study treatment, he/she should inform the investigator or study collaborator of the noncompliance with treatment at visit. The subject must return unused study medication and study medication sheets at visit.
4. The subject must not take any medications including over-the-counter products other than medications as instructed by the investigator without advance consulting (except for emergency).
5. If the subject consults other medical institution from the time of informed consent to the end of the follow-up period, notify the physician of medical institution of the subject's participation in this study.
6. If the subject consults other medical institution from the time of informed consent to the end of the follow-up period, notify the investigator of the circumstances and therapy.
7. The subject must visit the site under fasted conditions at Visits 2, 3 and 8 or Early Termination Visit. For visits serum chemistry test is scheduled, the subject visits the site under fasted conditions wherever possible.
8. Female subject of childbearing potential who is sexually active with a nonsterilized male partner must routinely use adequate contraception from the time of informed consent to the end of the follow-up period.

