9.1.12 Procedures for Clinical Laboratory Samples

The items of clinical laboratory tests are shown in [Table 9.a](#). Samples will be collected and handled in accordance with the separate operation manual. For clinical laboratory tests, the maximum volume of blood at any single visit is approximately 10 mL.

Table 9.a Clinical Laboratory Tests

Hematology	Serum Chemistry	
Red blood cells (RBC)	Albumin	Glucose (fasting or non-fasting) ^{a)}
White blood cells (WBC)	AST	Total protein
Hemoglobin	ALT	Potassium
Hematocrit	γ -GTP	Sodium
Platelets	Alkaline phosphatase	Calcium
Neutrophils	Total bilirubin	Chloride
Eosinophils	Direct bilirubin	Lipids (fasting or non-fasting) ^{a)}
Basophils	(Conjugated bilirubin)	Triglycerides
Lymphocytes	Creatinine	Total Cholesterol
Monocytes	Creatine kinase	High-density lipoprotein cholesterol
	Blood urea nitrogen (BUN)	Low-density lipoprotein cholesterol (direct measurement)
	Uric acid	
Hormonal Test (Visit 1 only)	Urinalysis	
Thyroid stimulating hormone (TSH) ^{b)}	Protein (qualitative)	Urine pH
Free T ₄ ^{b)}	Glucose (qualitative)	Microscopic examination ^{c)} (white blood cells, red blood cells, and casts)
	Occult blood (qualitative)	
Pregnancy test (female subjects of childbearing potential only)		
Urine human chorionic gonadotropin (hCG)		
Urine Drug Screening ^{d)}		
Amphetamines (including methamphetamine), barbiturates, benzodiazepines, cannabinoids, cocaines, morphines, phencyclidines, and tricyclic antidepressants		

- a) Blood will be collected under fasted conditions at Visits 2, 3 and 8 or Early Termination Visit. For other visits, blood will be collected under fasted conditions wherever possible.
- b) TSH will be measured at Visit 1, and when TSH value is outside the normal range, free T₄ will be measured. If a clinically significant abnormality of thyroid gland is found based on the results of TSH and free T₄, the subject will be excluded from the study.
- c) Microscopic examination will be performed if abnormality is found in any item in urinalysis.
- d) If the subject has a positive urine drug result, he/she will be excluded from the study. However, when the subject has a positive urine test result at Visit 1 because the urine test was performed prior to washout of pretreatment drug, the subject is eligible for the study if he/she has a negative drug test result at Visit 2.

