13.1.5 Safety Analysis

AEs

The definition of treatment-emergent adverse events (TEAE) will be described in the statistical analysis plan (SAP). TEAEs will be summarized using the safety analysis set. TEAEs will be coded using the MedDRA and will be summarized by system organ class (SOC) and preferred term (PT). No statistical testing or inferential statistics will be generated.

A subject who has developed a same TEAE more than once will be counted as 1 subject in the severity category corresponding to the maximum severity of the event.

Clinical Laboratory Test, Weight, Vital Signs, and ECG

Summary statistics of observed values and changes at each time point (values at each time point in the double-blind treatment period – baseline) will be calculated for clinical laboratory tests, vital signs, ECG parameters, and weight for each treatment group. Incidences of values that are outside normal ranges and are potentially and clinically significant will be calculated.

C-SSRS

Descriptive statistics of C-SSRS will be calculated at each time point for each treatment group.

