(21) Antiarrhythmics of class Ia, Ic	
(22) Antiulcer drugs	Omeprazole, cimetidine, and sulpiride are NOT allowed.
(23) Anticoagulants/antiplatelet treatment	Including low dose of aspirin as antiplatelet treatment. Low-molecular weight heparins are allowed as needed.
(24) Antidiarrheal agents	Loperamide, bismuth, and kaolin preparations are allowed.
(25) Antihistamines	Loratadine, desloratadine, cetirizine, levocetirizine, mizolastine, and fexofenadine are allowed.
(26) Antineoplastics	
(27) Hormones	Chronic use for contraception or treatment of benign prostatic hyperplasia are allowed.
(28) Hypoglycemic agents	Chronic use is allowed.
(29) Insulin	Chronic use is allowed without major change of dose or administration.
(30) Calcium antagonist	Chronic use is allowed without major change of dose or administration.
(31) Narcotic analgesics	Topical administration including for dental use is allowed.
(32) NSAIDs	Episodic use is allowed. Selective COX-2 inhibitors, acetaminophen, and topical NSAIDs are allowed.
(33) Cough/cold agents	Episodic use is allowed. However, chronic use of preparations containing ephedrine, pseudoephedrine, and codeine are NOT allowed for more than 1-week treatment.

MAOI = monoamine oxidase inhibitor, ADHD = attention deficit hyperactivity disorder,
NSAIDs = nonsteroidal anti-inflammatory drugs, COX-2 = cyclooxygenase-2

<Justification for Prohibited or Restricted Concomitant Medications>

- (1) was set since other investigational drug could influence the evaluation of the efficacy and safety.
- (2) was set since antidepressants could influence the evaluation of the efficacy. Especially, concomitant use of monoamine oxidase inhibitors (MAOIs) was prohibited because concomitant use of MAOIs could enhance serotonin action and influence the evaluation of the efficacy, and because the safety of subjects should be ensured.
- (3) was set since anxiolytics (tranquilizers) could improve anxiety which was known to an accompanying symptom of depression and influence the evaluation of the efficacy.
- (4) was set since hypnotics could improve insomnia which was known to an accompanying symptom of depression and influence the evaluation of the efficacy. Concomitant use of non-benzodiazepines was allowed as needed because the extent of anxiolytic and carry-over effects of non-benzodiazepines was relatively weak, and thus these effects had only a small influence on efficacy evaluation.

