9.1.12 Procedures for Clinical Laboratory Samples

The items of clinical laboratory tests are shown in [Table 9.a](#). Samples will be collected and handled in accordance with the separate operation manual. For clinical laboratory tests, the maximum volume of blood at any single visit is approximately 10 mL.

Table 9.a Clinical Laboratory Tests

Hematology	Serum Chemistry	
Red blood cells (RBC)	Albumin	Glucose (fasting or non-fasting) ^{a)}
White blood cells (WBC)	AST	Total protein
Hemoglobin	ALT	Potassium
Hematocrit	γ -GTP	Sodium
Platelets	Alkaline phosphatase	Calcium
Neutrophils	Total bilirubin	Chloride
Eosinophils	Direct bilirubin	Lipids (fasting or non-fasting) ^{a)}
Basophils	(Conjugated bilirubin)	Triglycerides
Lymphocytes	Creatinine	Total Cholesterol
Monocytes	Creatine kinase	High-density lipoprotein cholesterol
	Blood urea nitrogen (BUN)	Low-density lipoprotein cholesterol
	Uric acid	(direct measurement)
Hormonal Test	Urinalysis	
Thyroid stimulating hormone (TSH)	Protein (qualitative)	Urine pH
Free T ₄ ^{b)}	Glucose (qualitative)	Microscopic examination ^{c)}
	Occult blood (qualitative)	(white blood cells, red blood cells, and casts)

Pregnancy test (female subjects of childbearing potential only)

Urine human chorionic gonadotropin (hCG)

Urine Drug Screening^{d)}

Amphetamines (including methamphetamine), barbiturates, benzodiazepines, cannabinoids, cocaine, morphines, phencyclidines, and tricyclic antidepressants

- a) Blood will be collected under fasted conditions at Visits 3 and 8 or Early Termination Visit. For other visits, blood will be collected under fasted conditions wherever possible.
- b) When TSH value is outside the normal range, free T₄ will be measured. If a clinically significant abnormality of thyroid gland is found based on the results of TSH and free T₄, the subject will be excluded from the study.
- c) Microscopic examination will be performed if abnormality is found in any item in urinalysis.
- d) If the subject has a positive urine drug result, he/she will be excluded from the study. However, when the subject has a positive urine test result at Visit 1 because the urine test was performed prior to washout of pretreatment drug, the subject is eligible for the study if he/she has a negative drug test result at Visit 2.

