Visit	Scheduled Study Day (days)	Time Interval (days)	
		Study Day	Follow-up Day
Placebo lead-in	Study Day: -8	≤ -5	-
Baseline (Week 0)	Study Day: -1	-4 - 1	-
Week 8	Study Day: 56	$2 \leq$	< 8
Week 8 (LOCF)	-	$2 \leq$	< 8

DSST, PDQ-5

Visit	Scheduled Study Day (days)	Time Interval (days)	
		Study Day	Follow-up Day
Placebo lead-in	Study Day: -8	≤ -5	-
Baseline (Week 0)	Study Day: -1	-4 - 1	-
Week 1	Study Day: 7	2 - 10	< 8
Week 8	Study Day: 56	$11 \leq$	< 8
Week 8 (LOCF)	-	$2 \leq$	< 8

Laboratory Value, Weight, ECG

Visit	Scheduled Study Day (days)	Time Interval (days)	
		Study Day	Follow-up Day
Screening	Study Day: -22	≤ -12	-
Placebo lead-in	Study Day: -8	-11 - -5	-
Baseline (Week 0)	Study Day: -1	-4 - 1	-
Week 4	Study Day: 28	2 - 42	< 8
Week 8	Study Day: 56	$43 \leq$	< 8

Vital Sign, C-SSRS

Visit	Scheduled Study Day (days)	Time Interval (days)	
		Study Day	Follow-up Day
Screening	Study Day: -22	<= -12	-
Placebo lead-in	Study Day: -8	-11 - -5	-
Baseline (Week 0)	Study Day: -1	-4 - 1	-
Week 1	Study Day: 7	2 - 10	<8
Week 2	Study Day: 14	11 - 21	<8
Week 4	Study Day: 28	22 - 35	<8
Week 6	Study Day: 42	36 - 49	<8
Week 8	Study Day: 56	50 <=	<8

Others

- Duration of exposure to double-blind study drug (days): date of last dose of double-blind study drug – date of first dose of double-blind study drug + 1
- Double-blind study drug compliance (%): number of double-blind study drugs taken / duration of exposure to double-blind study drug × 100 (rounded off to one decimal place)
- $QT_{CF} \text{ interval} = (QT \text{ interval}) / ([QT_{CB} \text{ interval}]^2 / [QT \text{ interval}]^2)^{0.33}$ (rounded off to the whole number)
- Among the laboratory test items, the following data will not be included if it is from a postprandial specimen.
Glucose, lipids (triglycerides, total cholesterol, HDL cholesterol, LDL cholesterol [Direct method])
-

1 Study Subjects, Demographic, and Other Baseline Characteristics

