	(3) Number and Percentage of Subjects with Potentially Clinically Significant of ECG Parameters	(3) Frequency distributions of the results based on PCS Criteria during the entire post-dose period	expression
41		3.3.2.4 Summary of Columbia-Suicide Severity Rating Scale (C-SSRS)	New addition

[Appendix 2]Definition of PCS Criteria**Hematology and Serum Chemistry**

Analysis	Unit	Unit	Definition of PCS
Variable(s):	system		
Red blood cells	CV	$10^4/\mu\text{L}$	Measured value is ≤ 0.9 -fold of LLN or ≥ 1.1 -fold of ULN
	SI	TI/L	Measured value is ≤ 0.9 -fold of LLN or ≥ 1.1 -fold of ULN
White blood cells	CV	/uL	Measured value is ≤ 2800 or ≥ 16000
	SI	GI/L	Measured value is ≤ 2.8 or ≥ 16
Hemoglobin	CV	g/dL	Measured value is ≤ 0.9 -fold of LLN
	SI	g/L	Measured value is ≤ 0.9 -fold of LLN
Hematocrit	CV	%	Measured value is ≤ 0.9 -fold of LLN
	SI	Fraction of 1	Measured value is ≤ 0.9 -fold of LLN
Platelets	CV	$10^4/\mu\text{L}$	Measured value is ≤ 7.5 or ≥ 70
	SI	GI/L	Measured value is ≤ 75 or ≥ 700
Neutrophils	CV	%	Measured value is ≤ 15
	SI	%	Measured value is ≤ 15
Eosinophils	CV	%	Measured value is ≥ 10
	SI	%	Measured value is ≥ 10
Basophils	CV	%	Measured value is ≥ 5
	SI	%	Measured value is ≥ 5
Lymphocytes	CV	%	Measured value is ≤ 10 or ≥ 80

	SI	%	Measured value is ≤ 10 or ≥ 80
Monocytes	CV	%	Measured value is ≥ 20
	SI	%	Measured value is ≥ 20
Albumin	CV	g/dL	Measured value is ≤ 2.5
	SI	g/L	Measured value is ≤ 25
AST	CV	U/L	Measured value is ≥ 3 -fold of ULN
	SI	U/L	Measured value is ≥ 3 -fold of ULN
ALT	CV	U/L	Measured value is ≥ 3 -fold of ULN
	SI	U/L	Measured value is ≥ 3 -fold of ULN
ALP	CV	U/L	Measured value is ≥ 3 -fold of ULN
	SI	U/L	Measured value is ≥ 3 -fold of ULN
Total Bilirubin	CV	mg/dL	Measured value is ≥ 2
	SI	umol/L	Measured value is ≥ 34.2
Creatinine	CV	mg/dL	Measured value is ≥ 1.5 -fold of ULN
	SI	umol/L	Measured value is ≥ 1.5 -fold of ULN
Creatine Kinase	CV	U/L	Measured value is ≥ 2 -fold of ULN
	SI	U/L	Measured value is ≥ 2 -fold of ULN
Uric Acid	CV	mg/dL	Measured value is ≤ 0.7 -fold of LLN or ≥ 1.3 -fold of ULN

	SI	umol/L	Measured value is \leq 0.7-fold of LLN or \geq 1.3-fold of ULN
Glucose	CV	mg/dL	Measured value is \leq 0.7-fold of LLN or \geq 2.5-fold of ULN
	SI	mmol/L	Measured value is \leq 0.7-fold of LLN or \geq 2.5-fold of ULN
Potassium	CV	mEq/L	Measured value is \leq 3.0 or \geq 5.5
	SI	mmol/L	Measured value is \leq 3.0 or \geq 5.5
Sodium	CV	mEq/L	Measured value is \leq 125 or \geq 155

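### The SAP removes every non-fasted serum glucose value from the PCS tables, although fasting at Week 4 is only a best-effort request

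*Protocol*

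**What the plan says.** **Fasting.** In the current protocol edition, Section 9.1.12, Table 9.a note a) says: "Blood will be collected under fasted conditions at Visits 2, 3 and 8 or Early Termination Visit". The next sentence covers the remaining visits: "For other visits, blood will be collected under fasted conditions wherever possible". Section 7.4 gives subjects the matching instruction: "For visits serum chemistry test is scheduled, the subject visits the site under fasted conditions wherever possible". Under the Appendix A schedule the remaining laboratory visits are Visit 1 (screening) and Visit 6 (Week 4). Table 9.a itself lists glucose and lipids as fasting or non-fasting, so fed samples are foreseen.

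**Exclusion.** In the SAP, the Others list that follows the time windows says: "Among the laboratory test items, the following data will not be included if it is from a postprandial specimen". The items named are glucose, triglycerides, and total, HDL and direct LDL cholesterol. SAP Appendix 1 records the rule as a new addition in Version 2 and gives no further reason.

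**Tables affected.** SAP 3.3.1.1 plans five summaries: (1) descriptive statistics, (2) subject plots, (3) reference-range shift tables, (4) PCS frequencies over the whole post-dose period, and (5) PCS shifts from the whole pre-dose period to the whole post-dose period. The glucose PCS limits in SAP Appendix 2 are at or below 0.7 times the lower limit of normal, or at or above "2.5-fold of ULN".

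**Protocol commitment.** Section 13.1.5 says: "Incidences of values that are outside normal ranges and are potentially and clinically significant will be calculated". It makes no exception for fasting status.

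**The concern.** Dropping fed glucose from means and from comparisons with a reference range is ordinary data handling, because fed and fasted values are not comparable. A PCS table has a different purpose: it counts subjects who crossed a fixed limit at any time on treatment. The exclusion rule makes no distinction between these uses. It removes low as well as high glucose values, and it acts at one of the two scheduled on-treatment laboratory visits.

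The consequence is misclassification as well as a smaller sample. A subject with an extreme fed glucose at Week 4 and a normal fasted value at Week 8 stays in the PCS table and is shown as not meeting the criteria. Nothing in the table tells the reader that a value was set aside.

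The population is not closed to such values. Protocol Table 7.a allows chronic use of hypoglycemic agents, and for insulin it says: "Chronic use is allowed without major change of dose or administration".

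**Working it through.** The plan gives no figure on this point, so the check is a reading of the rules in sequence.

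**Step 1. Where can a fed sample arise without a deviation?**

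| Visit | Fasting rule (Table 9.a note a) | Role in PCS tables |
|---|---|---|
| Visit 1, screening | best effort | pre-dose side of (5) |
| Visits 2 and 3 | required | pre-dose side of (5) |
| Visit 6, Week 4 | best effort | post-dose, (4) and (5) |
| Visit 8 or early termination | required | post-dose, (4) and (5) |

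A fed Week 4 sample is therefore within protocol.

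**Step 2. Does the exclusion reach the PCS tables?** The rule stands among general definitions and names no table. Summaries (4) and (5) contain no wording that restores fed values. Read as written, it applies to all five summaries.

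**Step 3. Follow one hypothetical subject.** Week 4 glucose is fed and at or above 2.5 times ULN. Week 8 glucose is fasted and normal.

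- Under the SAP, the Week 4 value is removed. The Week 8 value is the only scheduled post-dose value left, so tables (4) and (5) class the subject as not meeting PCS.
- Under protocol 13.1.5 as worded, the Week 4 value belongs in the incidence.

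The two documents give different answers for the same data.

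**Step 4. The pre-dose side of table (5).** A fed screening glucose beyond the limits is removed in the same way, so a subject could be shown as not meeting PCS before treatment. Exclusion criterion 22 narrows this case, because clinically significant laboratory abnormalities bar entry.

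**Step 5. Do other outputs supply the same count?**

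- *Adverse events.* Under protocol 10.1.3 a laboratory change is an AE only if it is judged clinically significant: action is needed, or the investigator considers it beyond normal fluctuation. It would then appear by arm in the tables of SAP 3.1.2. That count depends on judgement, whereas PCS applies a fixed limit.
- *Urine glucose.* SAP 3.3.1.2 gives shift tables at each post-dose visit. The categories run from negative to 5+ with no PCS limit, so they cannot show a low serum glucose.

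Neither output is a fixed-limit serum count.

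**Step 6. Size.** The number of affected subjects depends on the share of Week 4 samples taken fed and on how often those samples cross the limits. The documents give neither. The count could be zero.

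**The case against.** The best case for the plan is that the loss is narrow and partly covered. Subjects are asked to fast wherever they can. Central laboratory results go back to the investigator for review, and a significant abnormality becomes an AE that is tabulated by arm. The PCS table pools the post-dose period, so the fasted Week 8 or early-termination value still contributes. Exclusion criteria 19 and 22 keep out unstable metabolic illness and clinically significant laboratory abnormalities at entry. Protocol 13.1 leaves analysis detail to the SAP. SAP 1.1.6.2 also plans a by-arm tabulation of excluded data, and its categories, set in a separate rules document, may or may not include postprandial values.

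Most of this stands and limits how far the point goes. It does not answer the misclassification: pooling does not bring back a removed value, and AE reporting applies a different test.

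Several stronger readings are tempting, and the documents do not support them:

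- *Gross fed abnormalities are never counted by arm.* They can be, through the AE tables, and urine glucose is tabulated separately.
- *Fasting at Week 4 is optional and the fasted group is self-selected.* The text makes a best-effort request. Nothing ties fasting to treatment arm in this double-blind trial. Early-termination samples on Days 2 to 42 also fall in the Week 4 window, and fasting is required for them.
- *Early leavers lose all their metabolic data.* That needs a fasting deviation or a missed early-termination visit.
- *The cholesterol exclusions are wrong.* That rests on outside knowledge of how meals affect cholesterol, which the documents do not supply.
- *A stated share of Week 4 data is lost.* Any share would be a guess.

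**Conclusion.** The point holds in a narrow form and is a cheap improvement. Read literally, the SAP removes fed serum glucose values from PCS tables (4) and (5), although the protocol foresees fed samples at Week 4 and promises incidences of such values without a fasting exception. A subject whose only value beyond the limits was fed would be reported as not meeting PCS. The primary endpoint and all efficacy results are unaffected.

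This rests on two readings: that the rule applies to every laboratory table because it names none, and that the Handling Rules for Analysis Data, which were not available, do not say otherwise. No magnitude is claimed.

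**What to change.** Amend the SAP as follows:

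1. In the Others rule, keep the postprandial exclusion for summaries (1) to (3) of 3.3.1.1, and leave the lipid exclusion as it is.
2. In PCS tables (4) and (5), include all serum glucose values and flag those from fed samples, or show the counts with and without them.
3. Report the number of values excluded as postprandial, by arm and visit.
4. Write serum glucose in the rule, so that it is not read as covering urine glucose.

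The cost is SAP wording, a flag and one small table. No new sampling is needed, and the existing rule already presupposes that postprandial specimens can be identified. The downside is that an occasional glucose value raised by a meal may be counted as PCS, but the flag will show it.

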9.1.13 Contraception and Pregnancy Avoidance Procedure

From signing of informed consent, throughout the duration of the study, to the end of the follow-up period, female subjects of childbearing potential (e.g., non-sterilized or premenopausal female subjects) who are sexually active with a nonsterilized male partner must use adequate contraception. Subjects will be provided with information on acceptable methods of contraception as part of the subject informed consent process and will be asked to sign a consent form stating that they understand the requirements for avoidance of pregnancy during the course of the study. During the course of the study, regular urine human chorionic gonadotropin (hCG) pregnancy tests will be performed, and subjects will receive continued guidance with respect to the avoiding pregnancy as part of the study procedures ([Appendix A](#)).

At visits when pregnancy tests are performed, subjects must be confirmed of having a negative urine hCG pregnancy test, as well as at the follow-up examination.

